as illustrated in Figure 2

Thus, FODMAP restriction has been proposed as a treatment for IBS and has been documented to be efficient in the majority of patients [14-17] In a recent study from Sweden, the effect of FODMAP reduction in IBS patients was seen, but not superior to alternative, standard treatment [18]. In clinical practice, FODMAP restriction is performed under the guidance of a clinical dietician. The first step is usually to record the patient's diet, exclude all food items with high FODMAP content from diet, followed by a structured re-introduction again under close guidance of a clinical dietician. FODMAP restriction done by patients themselves after written or online guidance lacks scientific support. FODMAP restriction has been included in the most recent NICE guidelines (NICE guideline CG61Irritable bowel syndrome in adults www.nice.org.uk).

A low FODMAP diet may also have impact on faecal microbiota. A recent study in IBS patients indicates that the responsiveness to a low FODMAP diet may be predicted by the microbiota profiles[19].

Although FODMAP reduction may play a role in patients with diet treated coeliac disease, there are no published studies addressing this topic. In fact, there is a huge knowledge gap and unmet clinical need for studying FODMAP in other patient populations than those suffering from IBS.

3. Hypotheses, aims and objectives

The overall aim is to improve dietary treatment of coeliac patients with persistent gastrointestinal symptoms in spite of a strict gluten free diet.

The project has two main objectives:

- A) To investigate the prevalence of persistent gastrointestinal symptoms and assess the amount of FODMAP in the diet of coeliacs on a strict gluten free diet. This will be done with a web-based quest back tool in collaboration with the Norwegian Coeliac Association.
- **B)** To perform a randomized, controlled trial in coeliac disease patients with gastrointestinal symptoms, comparing a low FODMAP glutenfree approach to an ordinary gluten free diet. This part of the project will also validate questionnaires and biomarkers for the assessment of gluten-free diet adherence.

In addition, the present project will provide unique biological materials for biobank and ongoing projects in our coeliac group. This is basic and translational research and is beyond the scope of this application.

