4.1. Project design, method selection and analyses

Study A: Prevalence of persistent GI-symptoms in coeliac disease

Setting

We have a rather unique situation in Norway as the majority of patients with coeliac disease are or have been members of the NCF, and communication electronically and on social media like Facebook is widespread. This will give us the opportunity to perform an online survey as, in fact, has been done in Canada [26]. However, in the mentioned study they did not record on going symptoms. Persistent symptoms has more recently been evaluated in a Finnish study using direct patient contact and written formulas [10]. We propose to use a web-based technology to interact with as many coeliac disease patients as possible.

Design

A national cross-sectional study exploring prevalence of persistent symptoms in treated coeliac patients.

Patients

Members of NCF will receive e-mail invitation to participate in the online survey, as well open invitations in relevant social media that target the coeliac disease population. This method gives the opportunity to include a large sample, and since we aim to obtain the number of participants needed for study B, the number of participants in this part of the project will be unlimited within the following inclusion criteria:

- Biopsy verified coeliac disease patient, 18-75 years of age
- Strict gluten free diet for at least 12 months

NCF has approximately 10 000 members. We expect a 30 % response rate, and aim to include 3000 patients in this study.

Methods

We will use web-based questionnaires to survey gastrointestinal symptoms, health related quality of life and diet adherence by questionnaire.

For recording of gastrointestinal symptoms we will use a published and validated questionnaire that was originally developed for IBS purposes, the Gastrointestinal Symptom Rating Scale, IBS version (GSRS-IBS) [27]. We, and others, have found that this form is very well suited to evaluate the burden of disease and symptom level for IBS-like symptoms in treated coeliac disease, and it is suitable for measuring the effect of interventions [28]. The questionnaire is translated to Norwegian. FODMAP intake will be estimated by use of a questionnaire developed by [name] & co-workers [29].

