In the current project we will employ recently developed disease specific quality of life forms. First, the Coeliac Disease Questionnaire (CDQ), a disease specific health related quality of life measure for adults with coeliac disease [30]. The form is translated into Norwegian, but has not been tested. Second, the Coeliac Symptom Index (CSI) was published by our collaborator in US, professor [name] at Harvard University, Boston [31]. This questionnaire is already translated and approved by the Harvard group. The project will include testing and validation of these disease specific tools for coeliac disease. Other relevant questions may add to the survey by NCF.

This study will also enable us to compare the collected information between CD patients with and without persistent GI-symptoms. Those patients who score high on the reported outcomes, will, as part of the survey, be invited to participate in study B.

Study B. A randomized controlled trial in patients with persistent GI-symptoms

Design

We will follow recommendations for design of clinical trials evaluating dietary interventions in patients with persistent functional gastrointestinal disorders [32]. A cross-over design has been carefully considered but is not possible as patients cannot be de-educated. A flow-chart of the study is given in Figure 3.

Patients

CD patients selected from study A, and willing to continue to study B

Inclusion criteria

- Coeliac patients (18-75 years) treated with GFD for at least 12 months
- Normal CD serology and duodenal biopsy (Marsh 0-1)
- Persistent gastrointestinal symptoms defined by GSRS-IBS score of 30 or more
- Strictly adherent to GFD
- Living less than 2 hours from study centre

Intervention

• Both groups will follow strict gluten free diet (GFD). The intervention group will in addition receive instructions on how to follow a FODMAP diet (LFD).

Endpoint

- Primary endpoint will be change in gastrointestinal symptoms measured by GSRS-IBS score.
- Secondary endpoints will be changes in biomarkers like serology and faecal microbiota

01.06.2018

Adherence

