Adherence to the diets will be monitored halfway in both groups. Assessment of dietary FODMAP and gluten intake will be obtained by 24-hour recall, which is a validated method for nutritional assessment in nutrition research [32]. Nutritional calculations will be done by the software Dietist Pro, which is implemented and used by dieticians at Oslo University Hospital, as well as in the other Nordic countries (www.kostdata.se/nb/dietist-net/dietist-net-pro).

Differentiated FODMAP calculations will be done by the software FoodWorks by our collaborators at the Monash University, Melbourne. To date, they are the only site that has a reliable FODMAP database based on food analysis.

Dietary assessment will also include evaluation of dietary adherence to the gluten-free diet by standardized dietician interview and by the coeliac disease adherence test (CDAT) [34]. There are few objective measures for diet adherence and the Norwegian translated CDAT version is not tested or implemented in Norwegian practice.

We will validate the CDAT questionnaire and recently suggested blood based tests for mucosal damage, the S-Intestinal Fatty Acid Binding Protein (S-IFABP) [35] and the faecal 33-mer peptide as a measure for gluten contamination [36]. Both these novel tests will be implemented at our clinical unit during 2018.

Figure 3 Flow-chart of study B. LFD: Low FODMAP diet. GFD: Gluten free diet

All partisipants will be offered follow-up visits for re-introduction of FODMAPS (intervention group) or instructions for LFD (control group).

Power calculation:

The primary endpoint for measuring effect of the low FODMAP diet will be GSRS-IBS total symptom score. From previous studies with coeliac disease patients and non-coeliac gluten sensitivity persons we know that a clinical significant difference in symptom score is present when group means are 22,5 (SD 8) and 29,5 (SD 11), respectively (based on our unpublished results from on going clinical trial). With a power of 80 % and a significance level of 0,05 we will need 31 patients in each group. To account for 15 % drop out, we aim to include 72 individuals.

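### Study B sets no entry condition on current FODMAP restriction, although Study A estimates FODMAP intake, so the contrast between the diets may be diluted

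*Protocol*

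**What the plan says.** Objective B (Protocol section 3) sets a low FODMAP gluten-free diet against a usual gluten-free diet. The Study B inclusion criteria (section 4.1) are five: "Coeliac patients (18-75 years) treated with GFD for at least 12 months"; normal serology and biopsy; a GSRS-IBS score of at least 30; strict gluten-free adherence; and residence within two hours of the centre. None mentions present or past FODMAP restriction.

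Study B patients come from Study A, where "FODMAP intake will be estimated by use of a questionnaire". Invitation to Study B depends on high reported-outcome scores; FODMAP intake is not named as a selection variable. Within Study B, FODMAP intake appears under Adherence, which is monitored halfway through. The primary endpoint is change in GSRS-IBS.

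The power statement takes as its target "group means are 22,5 (SD 8) and 29,5 (SD 11), respectively", and concludes "With a power of 80 % and a significance level of 0,05 we will need 31 patients in each group". Enrolment is then raised: "To account for 15 % drop out, we aim to include 72 individuals".

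**The concern.** The trial tests what happens when FODMAPs are removed from the diet. A patient who has already removed most of them, and still has symptoms, meets every listed criterion. In the low FODMAP arm the instruction would change little for that patient, and the arm's mean improvement would be pulled towards zero. In the control arm the same patient is not on the usual gluten-free diet that objective B names as comparator.

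The criteria are careful about gluten-free status, which both arms share, and silent on the diet that is randomised. The protocol's own reasoning makes the omission harder to defend: it rules out a cross-over because dietary teaching cannot be undone. Knowledge of the low FODMAP diet acquired before entry cannot be undone either.

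At stake is the reading of a null or weak result, which could reflect either an ineffective diet or too little contrast. Once patients are enrolled, the achieved contrast can be described but not restored.

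**Working it through.** **Inputs** (Protocol section 4.1, power calculation): means 22.5 and 29.5, so δ = 29.5 − 22.5 = 7.0; SDs 8 and 11; α = 0.05; power 80 %; 31 per arm. Sidedness is not stated. Two-sided is assumed because it reproduces the stated number; one-sided gives 24 per arm.

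**Reproducing the plan's figure.**
- Common SD = √((8² + 11²)/2) = √(185/2) = 9.62.
- Normal approximation: n = 2 × (9.62 × (1.960 + 0.842)/7)² = 29.6, rounded up to 30 per arm.
- Noncentral t: power is 79.2 % at 30 per arm and 80.5 % at 31. The stated 31 is therefore right for these inputs.
- Dropout: 62 × 1.15 = 71.3, rounded up to 72, as stated. Dividing instead, 62/0.85 = 72.9, gives 73. The difference is immaterial here.

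**Dilution model.** Let f be the share of patients who already restrict FODMAPs and g the fraction of the full benefit they still obtain from the instruction. The mean difference becomes δ(f, g) = 7 × (1 − f × (1 − g)). Power at 31 per arm comes from the noncentral t with 60 degrees of freedom and noncentrality δ/(9.62 × √(2/31)) = δ/2.443. Both f and g are assumptions; the documents give neither.

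| f | δ, no gain (g = 0) | power | δ, half gain (g = 0.5) | power |
|---|---|---|---|---|
| 0 % | 7.00 | 80.5 % | 7.00 | 80.5 % |
| 10 % | 6.30 | 71.8 % | 6.65 | 76.4 % |
| 20 % | 5.60 | 61.6 % | 6.30 | 71.8 % |
| 30 % | 4.90 | 50.6 % | 5.95 | 66.9 % |

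Allowing for the extra spread that a mixture of responders and non-responders creates in the low FODMAP arm (variance 64 + f(1 − f) × 49) lowers the no-gain figures slightly, to 70.8 %, 59.8 % and 48.5 %.

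**Reserve.** On the normal approximation, which gives 81.7 % at 31 per arm, power drops below 80 % once f passes about 2.3 % with no gain. Regaining 80 % by numbers alone, on the same approximation, would take 37 per arm at f = 10 % (74/0.85 = 87.1, so 88 enrolled) or 47 per arm at f = 20 % (94/0.85 = 110.6, so 111 enrolled), against the planned 72.

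**The case against.** Several counter-arguments have force.

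- **Frequency.** A reader might infer that the contrast is diluted and that 80 % power is missed. The documents do not support that: they give no share of restrictors, and at 0 % there is no loss. Nor does section 2.1 report that coeliac patients restrict on their own. It says "FODMAP restriction done by patients themselves after written or online guidance lacks scientific support", in a paragraph about IBS treatment. That is a statement about evidence, not about how common the practice is.
- **Zero gain is the worst case.** The same sentence separates self-directed from dietitian-guided restriction, so a self-restrictor might still benefit from proper guidance. This stands, and is why the half-gain column is shown.
- **Which arm is affected.** A reader might infer that both arms shrink the difference. With change from baseline as endpoint, a control patient who restricted before entry already carries any effect in the baseline score, and no further change is expected. The dilution arises in the low FODMAP arm.
- **The 7 points.** The source is described thus: "From previous studies with coeliac disease patients and non-coeliac gluten sensitivity persons we know that a clinical significant difference in symptom score is present". It is not an effect of the diet in people with unrestricted intake, and the SDs are for scores, not changes. Scaling it by the share of restrictors illustrates sensitivity; it does not forecast power.
- **Partial safeguards.** The threshold of 30 removes patients whose own restriction worked, and 24-hour recall lets the achieved FODMAP contrast be examined. Both help, but neither keeps already restricting patients out.
- **Other text.** The flow chart (Figure 3) and some text after the power calculation could not be read in the copy reviewed, so a condition stated there cannot be excluded. The inclusion list itself is complete under its heading.

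**Conclusion.** The design gap holds: as written, the entry criteria admit patients who already follow the diet under test, although the trial will hold an estimate of their intake before they are invited. The consequence is conditional. If 10 % to 30 % already restrict, power at 31 per arm would be about 72 % to 51 % with no gain and about 76 % to 67 % with half the gain. This assumes a 7-point effect in everyone else, unchanged SDs and a two-sided test at 0.05. The sample size calculation is not wrong on its own inputs. This is a cheap improvement, not an error in the stated power.

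**What to change.** Add one line to the Study B inclusion criteria: *Not currently following a low FODMAP diet, screened from the Study A FODMAP questionnaire and confirmed in the dietitian interview before randomisation.* If an intake cut-off is used, the investigators should set it in advance; the documents offer no basis for choosing one here.

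The sample size need not change, and the screening data are already collected. The costs are a somewhat smaller pool and a result that applies only to patients not already restricting. For scale, the prevalences quoted in section 2.1 (10 % to 23 %) applied to the 3000 planned respondents give 3000 × 0.10 = 300 to 3000 × 0.23 = 690 symptomatic candidates. That is an upper guide: those prevalences are not stated to be defined by a GSRS-IBS score of 30 or more, and the travel, biopsy and consent conditions will reduce the number further.

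### Primary endpoint is worded as change in one place and as total score in the other, the 80% power rests on raw-score SDs only, and the 7-point difference is not shown to be a known important one

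*Protocol*

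**What the plan says.** All references are to the protocol, section 4.1, Study B, unless stated.

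- **Endpoint:** "Primary endpoint will be change in gastrointestinal symptoms measured by GSRS-IBS score".
- **Power calculation:** "The primary endpoint for measuring effect of the low FODMAP diet will be GSRS-IBS total symptom score". Change is not mentioned there.
- **Target difference:** it is introduced with "From previous studies with coeliac disease patients and non-coeliac gluten sensitivity persons we know that a clinical significant difference" in symptom score, which "is present when group means are 22,5 (SD 8) and 29,5 (SD 11), respectively". The source is given as "based on our unpublished results from on going clinical trial".
- **Size:** "With a power of 80 % and a significance level of 0,05 we will need 31 patients in each group". Allowing for 15% drop-out, the aim is 72 patients.
- **Comparison to be made** (section 3, objective B): a "randomized, controlled trial in coeliac disease patients with gastrointestinal symptoms, comparing a low FODMAP glutenfree approach to an ordinary gluten free diet".
- **Entry threshold on the same scale:** "Persistent gastrointestinal symptoms defined by GSRS-IBS score of 30 or more".

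**The concern.** There are two linked difficulties.

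First, the endpoint line and the power paragraph do not describe the same variable. Under randomisation, change and end-of-intervention score have the same expected between-arm difference, but not the same SD, so they do not have the same power. The figures 8 and 11 are SDs of scores. If the primary comparison is of change, the SD that matters is one the protocol does not give. Until one version is fixed in both places, either could later be presented as primary.

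Second, the 7 points are presented as something already known to be clinically significant. They are a gap between two diagnostic groups. The trial asks whether two diets differ within one of those diagnoses, in patients selected for high scores. Both source means, 22.5 and 29.5, lie below the entry threshold of 30, so the source groups as a whole are not the population to be enrolled.

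The power paragraph is the only justification of the trial size in the text at hand. A reader will take from it both the 80% and the 7 points as a yardstick for the result.

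**Working it through.** **Inputs.** Means 22.5 and 29.5, SDs 8 and 11, 31 per group, 80% power, significance level 0.05 and 72 enrolled with 15% loss all come from the power paragraph. Sidedness is not stated. Two-sided is assumed, because a one-sided calculation gives 24 per group (normal approximation), which does not match.

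**1. Reproduce the plan's figure.**
- Difference: 29.5 − 22.5 = 7.0.
- Pooled SD: √((8² + 11²)/2) = √92.5 = 9.62.
- Standardised difference: 7/9.62 = 0.728.
- Two-sample t test, noncentral t, 60 df: noncentrality 7/(9.62 × √(2/31)) = 2.87. Power is 80.5% at 31 per group and 79.2% at 30.

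The stated 31 is therefore correct, and it is the size for a comparison of raw scores.

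**2. What 31 per group gives in general.** Power of 80% corresponds to a standardised difference of 0.723, whichever score is analysed. Seven points therefore reaches 80% if the SD of the analysed quantity is at most 7/0.723 = 9.68. One df fewer, for a baseline covariate, leaves this at 9.68.

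| SD of analysed score | Difference detectable with 80% power | Power for 7 points, unadjusted |
|---|---|---|
| 8 | 0.723 × 8 = 5.8 | 92% |
| 9.62 | 0.723 × 9.62 = 7.0 | 80.5% |
| 11 | 0.723 × 11 = 8.0 | 69% |

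**3. What each version of the endpoint needs.** Write s_b and s_f for the baseline and follow-up SDs and r for their correlation.
- Follow-up score: SD = s_f.
- Change: SD = √(s_b² + s_f² − 2·r·s_b·s_f).
- ANCOVA: residual SD = s_f·√(1 − r²).

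The protocol gives neither s_b nor r for the enrolled patients, so the SD of change cannot be computed from it.

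The ANCOVA residual SD can be bounded: it is never larger than s_f. With s_f = 9.62 it is at most 9.62, which is below 9.68. Power for 7 points is then at least 80% at any r (80.5% at r = 0, after the loss of one df).

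The residual SD is also never larger than the SD of change, because a change score fixes the baseline slope at 1 while ANCOVA estimates the slope that minimises the residual variance. All three versions estimate the same treatment effect.

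**4. Can n = 72 stay?** 72 × 0.85 = 61.2 completers. With 30 and 31 completers the plan's own calculation gives 79.8%, so nothing here calls for a different n.

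**5. Source and use of the 7 points.** No arithmetic applies. The source contrast is coeliac disease against non-coeliac gluten sensitivity; the trial contrast is low FODMAP plus gluten-free against gluten-free, both arms coeliac, all at 30 or more on entry. The protocol cites no minimal important difference for GSRS-IBS and does not link the gap to an effect of diet.

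**The case against.** The best reply is that there is no real contradiction: the power paragraph says which score, the endpoint line says it is followed over time, and together they mean change in total score. That is the natural reading, and it stands. It settles the wording but not the power, since 8 and 11 are still not SDs of change.

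A second reply is that the choice between change, follow-up score and ANCOVA is commonly left to the SAP, which may exist. This also has force. A missing model is not the complaint. The complaint is that the protocol fixes an endpoint and a sample size that rest on different variables. ANCOVA is offered because it removes the mismatch using a baseline score that a change endpoint already requires.

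A third reply is that relabelling the 7 points changes no sample size, datum or decision. That is right, so it is only a minor wording point. The source is unpublished, so one can say only that support is not shown, not that 7 points is unimportant.

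A reader might go further and infer that the trial is underpowered, or that ANCOVA buys a definite number of percentage points over change. The documents support neither. With follow-up SD 9.62 and an assumed r of 0.3, change-score power for 7 points is 84%, 78% or 66% for assumed baseline SDs of 3.64, 6.54 or 9.62. None of those inputs is in the protocol, and selecting patients at 30 or more may also shrink the follow-up SD. These figures show that the answer is undetermined; they do not measure a loss. Nor do source means below 30 prove underpowering, since scores may fall in both arms by the end of the intervention.

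**Conclusion.** The point holds as a mismatch to be settled; it is not a demonstrated shortfall.

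The arithmetic of the power paragraph is sound for a raw-score comparison with SD about 9.62. Read as change in total score, the stated endpoint has no SD of change or baseline correlation behind its 80%, and true power may lie above or below that figure. Across the protocol's own two SDs, unadjusted power for 7 points runs from 92% to 69%.

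Adjusting for baseline keeps power at about 80% or more whatever the correlation, provided the follow-up SD is no larger than about 9.7. That proviso is an assumption about the enrolled population which the protocol cannot confirm.

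The statement that 7 points is a known clinically significant difference is not supported for two diets within coeliac patients enrolled at 30 or more. This part is an overstatement and alters no result.

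**What to change.** Keep n = 72.

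1. **One primary analysis, stated identically under Endpoint and under Power calculation:** the between-arm difference in end-of-intervention GSRS-IBS total score, by ANCOVA adjusted for the baseline total score. This estimates the same treatment effect as change.
2. **Power stated as conditional:** 31 completers per arm give 80% power (two-sided 5%) for about 0.72 times the residual SD of the follow-up score, so 7 points is covered if that SD is about 9.7 or less. Add the unadjusted power for 7 points: 92% at SD 8, 80.5% at SD 9.62 and 69% at SD 11.
3. **Minor wording:** describe 7 points as an assumed target difference and name the groups it came from. This corrects the overstatement; it does not show that 7 points is relevant or attainable.

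The cost is rewording one endpoint line and one paragraph before outcome data are examined by arm. No patients, visits or measurements are added. The one drawback is that the stated power becomes openly conditional on an SD.

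### Are 72 patients too few to leave 31 per group after 15% drop-out?

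*Protocol*

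**What the plan says.** The paragraph on power for Study B (Protocol, section 4.1) bases the size on the total GSRS-IBS score. It takes as clinically significant a difference in which "group means are 22,5 (SD 8) and 29,5 (SD 11), respectively", figures drawn from the group's own unpublished results. From these it concludes: "With a power of 80 % and a significance level of 0,05 we will need 31 patients in each group". The next sentence sets the recruitment target: "To account for 15 % drop out, we aim to include 72 individuals". The paragraph does not name the test, say whether it is one- or two-sided, or give the formula used to allow for drop-out.

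**The concern.** An allowance for drop-out is meant to leave the required number of patients after the expected loss. The usual method divides the requirement by the share retained: 62 / 0.85 = 72.9. A common slip is to multiply by one plus the drop-out rate instead, which is always too small: 62 x 1.15 = 71.3, or 31 x 1.15 = 35.65 per arm. Rounded up to equal arms of 36, that gives exactly the stated 72. With the protocol's 31 per group, 15% and 72 side by side, the expected number of completers falls just under the requirement.

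Because 31 is the smallest whole number per group that reaches 80% power, there is little slack. If the shortfall were real and sizeable, the trial would recruit to a target that could not deliver its stated power.

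**Working it through.** **Inputs**, all from the power paragraph in section 4.1: means 22.5 and 29.5, SDs 8 and 11, power 80%, significance level 0.05, 31 per group, drop-out 15%, target 72. Two-sided testing is assumed because the text does not say.

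**Step 1: reproduce the 31.**
- Difference: 29.5 − 22.5 = 7.
- Pooled SD: √((8² + 11²)/2) = √((64 + 121)/2) = 9.618.
- Normal approximation: n = 2 × (9.618 × (1.960 + 0.842) / 7)² = 29.63, so 30 per group.
- Two-sample t-test (noncentral t): 30.62, so 31 per group. This matches the protocol.
- One-sided testing would give 24 (normal approximation), which does not match, so the two-sided assumption is reasonable.

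**Step 2: inflate for 15% drop-out.**

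| Starting point | Calculation | Result |
|---|---|---|
| Rounded total, divide | 62 / 0.85 | 72.94, so 73 |
| Rounded per arm, divide | 31 / 0.85 | 36.47, so 37 per arm (74) |
| Rounded per arm, multiply | 31 × 1.15 | 35.65, so 36 per arm (72) |
| Unrounded total, divide | 2 × 30.62 / 0.85 | 72.06 |

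The stated 72 follows from the multiplying slip. It is also the correct division applied to the unrounded requirement and rounded to the nearest whole number. The document does not allow a choice between the two.

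**Step 3: completers from 72.**
- Expected: 72 × 0.85 = 61.2, or 30.6 per arm.
- Against the rounded 62: short by 0.8 patient. Keeping 62 permits 10 losses: 1 − 62/72 = 13.9%.
- Against the unrounded 61.25: short by 0.05 patient. Permitted loss: 1 − 61.25/72 = 14.9%.

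**Step 4: power** (two-sided t-test, difference 7, SD 9.618).

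| Completers | Power |
|---|---|
| 31 + 31 | 80.5% |
| 30.6 per arm | 79.97% |
| 30 + 31 | 79.8% |
| 30 + 30 | 79.2% |

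By the normal approximation, power at 30.6 per arm is 81.2%.

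**Step 5: compare with the uncertainty in the inputs.**
- If each patient drops out independently with probability 0.15, the number lost from 72 has standard deviation √(72 × 0.15 × 0.85) = 3.0. The gap of 0.8 is about a quarter of that.
- Using SD 8 for both arms, the normal approximation needs 21 per group. Using SD 11 for both, it needs 39. A one-patient discrepancy is small beside that range.

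**The case for a change.** The best argument for acting is that the protocol states 31, not 30.62, and the drop-out sentence builds on the stated number. Measured against its own requirement, 72 falls short whichever route produced it. The unrounded route does not fully rescue it either: 72.06 rounded up, as sample sizes normally are, gives 73. A correction would take one sentence.

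The literal arithmetic stands: 61.2 is below 62, and 73 or 74 is what strict rounding up gives. Two things do not stand. First, that the authors multiplied instead of dividing is an inference. It fits 72, but so does division followed by ordinary rounding. Second, the shortfall has no consequence for the trial. It exists only when a requirement already rounded up is treated as an exact threshold, and it costs 0.5 percentage points of power in expectation (80.5% to 79.97%), ending at the 80% the protocol claims.

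The possible corrections would also gain little. Replacing an assumed 15% with 13.9% gives false precision to a guess. Adding two patients would not protect the trial if the true loss or the true SD differed from plan by an ordinary amount.

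**Conclusion.** No change is needed. The plan delivers its stated power and drop-out allowance to within rounding: 72 patients cover between 13.9% loss (against 62) and 14.9% loss (against 61.25), and power after 15% loss is 79.8% to 80.0%. The target is one patient below strict rounding up in total, or two with equal arms. No estimate, test or conclusion depends on that.

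This rests on a two-sided two-sample t-test with pooled SD 9.618 and equal allocation, which is the reading that reproduces the protocol's 31 per group. It concerns only the step from 31 per group to 72. It does not assess whether the assumed means and SDs suit this population.
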